	For Aim 2c, the outcomes of interest are the metabolomic profile from blood samples obtained longitudinally.						
	For Aim 2d, pain scores , occurrence of infection , and antibiotic use will be obtained via a daily 4-week diary for evaluation of pain on an ordinal scale (0,1,2,,10), occurrence of infection symptoms, and use of antibiotics (type, duration, dose).						

Study Design	For this Phase II, single-blind, longitudinal controlled trial, the experimental design is a two-treatment, two-period, two-sequence cross-over design. The two treatment regimens are (A) infusion of G6PD-deficient donor units, and (B) infusion of G6PD-normal donor units. Due to the scarcity of G6PD-deficient units in the donor pool, we will exchange units that are available at the time of scheduled study exchange (likely normal units) and not utilize a randomization scheme. Each 4-week study exchange period will be separated from the second study exchange by a 4-month washout interval. During the washout period, we will look for suitable units (likely G6PD-deficient) for the second study exchange.
Sample	N = 16 eligible patients will be enrolled
Participation Time	Each enrollee's participation will last at least 6 months
Enrollment Time	Recruitment and enrollment of the participants will require 4 years

SCHEMA

Protocol: Single blind, randomized, crossover study

Figure 1: Study Schema: We will compare two treatment regimens via is a two-treatment, two-period, two-sequence cross-over design: CO(2,2,2). The two treatment regimens are (**A**) infusion of G6PD-deficient donor units, and (**B**) infusion of G6PD-normal donor units. The two sequences (**AB** and **BA**) will be assigned to the N=16 enrollees by RBC unit availability at the time of the first study exchange transfusion.

The two 4-week periods will be separated by a 4-month washout interval. The outcome measures of interest are 24-hour ⁵¹CR-labeled PTR of RBCs, and Hemoglobin A evaluated before and 4 weeks after infusion.

Period/ Procedure					Fo		Follow	-up visits			
Study Day/Visit Day	24-72 hrs pre- infusio n	Pre- transfusio n	5,7.5,10,12.5,15, 30 min post infusion	1 hr post transfusion/ infusion (+/-15 min)	24hr post infusion (+/- 3 hours)	48 hr post infusio n (+/- 3 hours)	72hr post infusio n (+/- 3 hours)	1week post infusio n (+/- 1 day)	2week post infusio n (+/- 2 days)	3 week post infusio n (+/- 2 days)	4 week post infusio n (+/- 2 days)
Informed consent	х										

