2 SPECIFIC AIMS

2.1 Primary Objective (Aim 1)

Aim 1. Evaluate the effects of blood from a donor with G6PD-deficiency on 24-hour post-transfusion recovery (PTR) as measured by Chromium 51 (⁵¹CR).

We hypothesize that, in contrast to the decreased PTR we found in healthy adult recipients, adults with SCD have a greater decrease in PTR when receiving older, stored RBCs from G6PD-deficient donors, as compared to G6PD-normal donors. We anticipate that the mean difference (i.e., the treatment effect) is larger than we observed in our previous study of healthy controls (6.8%).

The Aim 1 investigation will be considered a success if the confidence interval estimate for the treatment effect (i.e., the mean difference in PTR between G6PD-deficient donors and G6PD-normal donors) in SCD patients is not too wide. With an n = 16 participants with complete data, with a hypothesized difference in PTR of 10%, the chance of drawing a sample of patients that would yield a p-value smaller than α = 0.05 is 99%.

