4.8 Unit Selection, Identification, and Study Activities

At enrollment, basic features of patient medical and surgical histories (i.e. age, gender, past red cell transfusions, red cell phenotype) will be collected. The subject's eligibility status and ABO/RBC phenotype will be entered into the electronic data capture system (EDC). If eligible, the subject's first data of chromium labeling will be determined, and appropriate RBC units at the UNC transfusion service will be identified.

At a minimum, potential RBC units will be selected from the appropriate RBC unit inventory to ensure that the unit is: 1) ABO compatible with the subject, 2) D, Cc, Ee, and Kk matched to the subject (**rr, Ror, or RoRo phenotype)**, 3) stored in AS1, 4) sickle negative, 5) G6PD positive or negative based on testing. African black donor units will be preferred, but not required, for selection due to the known increased prevalence for G6PD deficiency. All other standard quality metrics for RBC units will be adhered to per standard blood bank service practice.

For G6PD testing: Two sterile segment links from the units assigned for the subject's red cell exchange identified by UNC will be codified and tested for G6PD enzyme activity in the clinical laboratory (McClendon Laboratories). Units identified as G6PD deficient/not deficient will be selected for use. Given the rarity of G6PD deficient units, these units will be selected first, if available. If not, a G6PD normal unit will be selected. Cross-matching for the unit with the subject will be done at UNC once the unit is 15-25 days old from collection, if possible.

Only study staff with the appropriate security level will be able to access the arm assignment (G6PD deficient first, or G6PD normal first). Access to case report forms containing information about the RBC products sent for each subject will also be restricted at the site to the appropriate study staff. Clinical staff overseeing the subject's participation in the trial, collecting data, and reporting the data into EDC will have access to the treatment arm assignment and information about the G6PD-status of the RBC products transfused.

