9.9 Sample Size Rationale

Given that the experimental design is a 2-treatment 2-period 2-sequence crossover, the number of patients enrolled should be an even number; thus, we will enroll N=16 participants and assign them depending upon RBC unit availability for the first exchange transfusion. The primary considerations in choosing N = 16 enrollees as the target sample size included:

- the anticipated frequency of missing data,
- o anticipated levels of precision of estimators,
- o anticipated levels of power of hypothesis tests,
- o costs and time requirements.

Our assessment of anticipated levels of precision and power focused on Aim 1. Those considerations were informed by a previous study⁷⁹ of 24-hour posttransfusion RBC recovery (PTR %), in which the point-estimates and interval-estimates of the population standard deviation (σ) of PTR were as follows:

Previous study ⁷⁹		Estimates of the mean		Estim	Estimates of σ	
	n	estimate	95%CI	estimate	95%CI	
Normal donors	27	85.3%	[84.1, 86.5]	3.2%	[2.5, 4.4]%	
G6PD-deficient	10	78.5%	[73.2, 83.7]	8.4%	[5.8, 15.3]%	

Precision of estimators of the means in Aim 1. The above table suggests conjectures about the magnitudes of standard errors (SE) of the means that can be anticipated for the proposed crossover study:

Proposed crossover study (n=16)	SE of the mean = SD/($16^{1/2}$)		
	Expected	Plausible Range	
A: units from normal donors	0.8%	[0.6, 1.1]%	
B : units from G6PD-deficient donors	2.1%	[1.5, 3.8]%	
A vs B : mean difference (if ρ =0.5) ¹	1.8%	[1.3, 3.4]%	
A vs B : mean difference (if ρ =0.0) ²	2.2%	[1.6, 4.0]%	
1 The SEs in the 3rd row correspond to	SD = 7.3% and [5.0.	13.61%.	

The SEs in the 3rd row correspond to SD = 7.3% and [5.0, 13.6]%.

2 The SEs in the 4th row correspond to SD = 9.0% and [6.3,15.9]%.

This table of SEs suggests that precision will be adequate for estimation of regimen-specific mean PTR% in the proposed crossover study of n=16 patients. For example, the width of the 95%Cl for the regimen-**A** mean is expected to be $\pm 1.6\%$ (i.e., 1.96 standard errors). The width of the 95%Cl for the regimen-**B** mean is

expected to be $\pm 4.2\%$, approximately. The third row in this table conservatively assumes that the correlation between a pair of PTR values is "moderate" (ρ =0.5). The fourth row's assumption (ρ =0) is ultra-conservative.

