Power of a test procedure in Aim 1. We consider a test of the null hypothesis that "The PTR(%) mean difference between regimens **A** and **B** is exactly zero in the target population of patients." If we assume that

- (1) the mean absolute PTR difference is Δ =10% in the target population of current and future SCD patients,
- (2) the SD of the differences in the target population is σ_{diff} =7.3% (or plausibly 5.0% $\leq \sigma_{\text{diff}} \leq 13.6\%$)
- (3) the correlation between paired PTR measures (for **A** and **B**) is $\rho = 0.50$ in the target population, and

(4) the sample size is n = 16 participants with complete data,

then the chance of drawing a sample of patients that would yield a p-value smaller than $\alpha = 0.05$ is 99%; this power level drops to 78% if $\sigma_{diff} = 13.6\%$. If $\Delta = 5\%$ and $\sigma_{diff} = 7.3\%$ in the target population, then the power level would be 72%; this power level drops to 28% if $\sigma_{diff} = 13.6\%$.

While the planned analysis strategy for Aim 1 will rely on a longitudinal linear mixed-effects model that accounts for period effects, the above estimates of anticipated precision and power are based on the assumptions of a simplistic model for paired 24hr PTR (%) outcomes. The resulting estimates are thus approximate but provide reasonable guidance about precision and power for the proposed study.

In summary, our sample size analysis suggests that a target enrollment of N=16 participants is adequate to provide satisfactory levels of precision for the estimators of mean PTR(%) and is expected to easily provide a high level of power for a test of difference when the treatment effect is near 10% or larger --even if a few participants do not have complete data. The estimates suggest that a smaller sample size would not provide adequate precision for key estimators (i.e., the confidence intervals would be too wide).

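### Nothing in the plan stops one G6PD-deficient donor supplying several participants, and the Aim 1 analysis has no donor term, so the primary confidence interval would be too narrow if donors recur.

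*Combined protocol and SAP*

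**What the plan says.** Aim 1 (2.1) concerns the effect on 24-hour recovery (PTR) of blood from a donor with G6PD deficiency. It counts as a success if the confidence interval for the mean difference is acceptably narrow. No numeric limit is given.

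Section 4.8 lists the minimum criteria for a study unit: ABO compatibility, Rh and K match within a restricted set of phenotypes, AS1 storage, sickle-negative status and the G6PD result. Donor identity is not among them. On priority it says: "Given the rarity of G6PD deficient units, these units will be selected first, if available". The Protocol Summary gives the reason for not randomizing: "Due to the scarcity of G6PD-deficient units in the donor pool". It also puts recruitment at 4 years.

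The Aim 1 model in 9.6 has terms for regimen, period and occasion, and none for donor or unit. The power calculation in 9.9 assumes that "the sample size is n = 16 participants with complete data" and treats these as simple paired outcomes.

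Section 4.8 also says that case report forms hold information about the red cell products sent for each subject, without itemizing it, and that unit labels are left unaltered. Section 14.4 asks for chain-of-identity records for the radiolabeled product. No section names a donor identifier as a data item or gives it a role in the analysis.

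**The concern.** G6PD status belongs to the donor. Generalizing to blood from deficient donors therefore needs replicate donors as well as replicate recipients. If one deficient donor supplies several participants, those participants share whatever is peculiar to that donor's cells, and their paired differences are correlated. An analysis that treats them as independent then understates the standard error.

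This matters more than usual here for two reasons. Section 9.6 makes point and interval estimates the main results. Section 2.1 judges success by interval width, and re-use slightly shrinks the reported interval while the true uncertainty grows, so it makes the criterion easier to meet.

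**Working it through.** **Inputs from 9.9.** SD of PTR is 8.4% for deficient donors and 3.2% for normal donors. There are n = 16 pairs. The correlation rho is 0.5 (base case) or 0 (the plan's most conservative case).

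**Inputs not in the documents, assumed here.** These are the number of distinct deficient donors and the share s of the deficient-regimen variance that is due to donors. A donor effect is placed in the deficient regimen only.

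**Step 1: the plan's own figures.** Variance of a paired difference = 8.4² + 3.2² − 2·rho·8.4·3.2.
- rho 0.5: 70.56 + 10.24 − 26.88 = 53.92, so SD 7.34 and SE 7.34/4 = 1.84 (plan: 7.3 and 1.8).
- rho 0: 70.56 + 10.24 = 80.80, so SD 8.99 and SE 2.25 (plan: 9.0 and 2.2).
- Two-sided paired t-test power, 15 df, for difference/SD of 10/7.3, 10/13.6, 5/7.3 and 5/13.6: 99.9, 78.5, 72.6 and 28.0% (plan: 99, 78, 72 and 28%).

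The plan's figures reproduce, under 16 independent pairs.

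**Step 2: true SE under re-use.** If deficient donor j supplies m_j participants,

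Var(mean difference) = [Var(diff) + (Σm_j²/16 − 1)·s·8.4²]/16.

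The multiplier (Σm_j²/16 − 1) is:
- 0 with 16 donors;
- 24/16 − 1 = 0.5 with 12 donors, four of them used twice;
- 32/16 − 1 = 1 with 8 donors, each used twice;
- 64/16 − 1 = 3 with 4 donors, each used four times.

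Example at rho 0 with each donor used twice:
- s = 0.3: √[(80.80 + 21.17)/16] = 2.5
- s = 0.5: √[(80.80 + 35.28)/16] = 2.7
- s = 0.8: √[(80.80 + 56.45)/16] = 2.9

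The SE with no re-use is 2.25.

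**Step 3: what the analysis would report.** The expected squared reported SE is [Var(diff) − (Σm_j²/16 − 1)·s·8.4²/15]/16. At rho 0.5, each donor used twice and s = 0.5:
- reported: √[(53.92 − 35.28/15)/16] = 1.80
- true: √[(53.92 + 35.28)/16] = 2.36

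The reported SE falls slightly below 1.84 while the true one rises.

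**Step 4: coverage of the usual paired 95% interval** (simulated; good to about one percentage point).

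| Deficient donors | rho 0, s = 30/50/80% | rho 0.5, s = 25/50/75% |
|---|---|---|
| 16, no re-use | 95/95/95 | 95/95/95 |
| 12, four used twice | 93/92/91 | 93/91/89 |
| 8, each used twice | 92/90/86 | 91/87/82 |
| 4, each used four times | 86/79/70 | 83/71/60 |

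With 8 donors, rho 0.5 and s = 30/50/75%, coverage is about 90/87/81%. The share stops at 75% there because a correlation of 0.5 carried by the non-donor part requires 1 − s ≥ 0.5² = 0.25.

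**Step 5: power.** At rho 0.5 and s = 0.5, a donor-level t-test has about 95% power for a 10-point difference with 8 donors and about 57% with 4. For a 5-point difference, power falls from 72% to about 45% with 8 donors.

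**The case against.** The best counter-argument is that re-use is possible but not shown. The Study Rationale puts exposure to deficient units at around 10%. The 15-25 day age window means that a recurring donor must have given separately and at a suitable time. The documents give neither of the two quantities that set the size. With only a few repeats the loss is a few points of coverage, and power for the 10-point difference holds up with 8 donors. Section 9.9 frames its target as a mean difference "in the target population of current and future SCD patients", which is about recipients, and calls its own model approximate. Section 9.6 plans sensitivity analyses on the covariance structure.

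Most of this stands as a limit on size and likelihood. It does not close the gap. The phenotype restriction narrows the pool, and 4 years gives donors time to recur. The covariance sensitivity analyses do not mention donors.

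A reader might also draw three stronger conclusions that the documents do not support:
- **That donor identity goes unrecorded, so re-use could never be detected.** The documents do not say either way. Product information is on the case report forms, labels stay intact and chain-of-identity records are required.
- **That the SD of 8.4% has one value per donor and so measures donor variation.** Section 9.9 gives only n, mean, SD and intervals. The Study Rationale describes the healthy-volunteer recovery work as autologous, where donor and recipient are the same person, so the SD cannot separate the two.
- **That donor characteristics differ systematically between regimens.** Section 4.8 says "African black donor units will be preferred, but not required, for selection", and applies this to all potential units. Normal units also come from tested units. Imbalance is possible but not shown, and the source of the normal units need not change.

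**Conclusion.** The point holds as a conditional weakness in the design and analysis. The plan permits donor re-use, does not state that a donor identifier is captured or used, and analyses the data as if every deficient unit came from a different donor. Any re-use with a real donor effect makes the primary interval too narrow.

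The size ranges from nothing (16 distinct donors) through a few points of coverage (four donors used twice) to coverage of 60 to 86% (four donors in all), depending on the assumed donor share and on rho. All of these figures rest on assumed donor numbers and shares. The plan's power for a 10-point difference is not overturned unless re-use is heavy. The validity of the interval is the main issue, because Aim 1 is judged on it.

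**What to change.** - In 4.8, record a coded donor identifier from the supplier for each study unit, and let each donor supply one study unit in the trial where feasible.
- In 9.6, state that if a donor recurs, the Aim 1 analysis will include a donor random effect, or a donor-clustered analysis will be made.
- Report the number of distinct donors per regimen with the Aim 1 results.

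The cost is one data field from the supplier and an occasional scarce deficient unit passed over. If all 16 deficient donors prove distinct, the planned analysis and the figures in 9.9 stand unchanged on this point.

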12 REGULATORY COMPLIANCE, ETHICS AND STUDY MANAGEMENT		
 12.1 ETHICAL STANDARD 12.2 REGULATORY COMPLIANCE 12.3 PRESTUDY DOCUMENTATION 13.4 INSTITUTIONAL REVIEW BOARD 13.5 SUBJECT CONFIDENTIALITY AND ACCESS TO SOURCE DOCUMENTS/DATA 13.6 PROTECTION OF HUMAN SUBJECTS 	39 39 39 39 40 41	
13.7 CHANGES IN THE PROTOCOL	41 41	
 13.7 CHANGES IN THE PROTOCOL 13.8 INVESTIGATOR COMPLIANCE	41 41	42
 13.7 CHANGES IN THE PROTOCOL	41 41 42 42 43 43 43 44 44	42

PROTOCOL SUMMARY

Title	The Impact of Oxidative Stress on Erythrocyte Biology						
Principal Investigator	[name] MD, MS						
Target Population	Adults with sickle cell disease who receive RBC transfusions						
Primary Objective	Aim 1. Evaluate the relative effects of blood from a donor with G6PD-deficiency on 24-hour post-transfusion recovery (PTR) as measured by Chromium 51 (⁵¹ CR).						
	Using a crossover experimental design, we will compare the two treatment regimens (G6PD-deficient vs. G6PD-normal donor units) in terms of the mean response on the ⁵¹ CR scale. The same approach will be used for Aims 2a – 2d.						
Secondary Objectives	Aim 2a. Evaluate the relative effects of blood from a donor with G6PD-deficiency on 4-week post-transfusion outcomes as measured by mean change in hemoglobin A .						
	Aim 2b. Evaluate the relative effects of blood from a donor with G6PD-deficiency on 4-week post-transfusion outcomes as measure by mean changes in twenty-three other clinically-relevant measures						
	Aim 2c. Evaluate the relative effects of blood from a donor with G6PD-deficiency on the longitudinal series of metabolic profiles obtained from blood samples.						
	Aim 2d. Evaluate the relative effects of blood from a donor with G6PD-deficiency on longitudinal pain scores , infection symptoms , and antibiotic use .						
Outcome Measures	For Aims 1and 2 the outcome measures of interest will be obtained from blood samples on 15 occasions within each of Period1 and Period2: At baseline prior to the infusion treatment. Post-infusion at 5, 7.5, 10, 12.5, 15, 30 minutes, and at 1, 24, 48, 72 hours, and at 1, 2, 3, 4 weeks.						
	For Aim 1, the outcome measure is 24-hour ⁵¹CR-labeled PTR of RBCs .						
	For Aim 2a, the outcomes are Hemoglobin A .						
	For Aim 2b, the outcome variables are 26 clinically-relevant measures.						

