4.6 Study Eligibility Criteria

*No waivers of protocol eligibility will be granted.

Inclusion Criteria

- 1. Age 18-60 years
- 2. A diagnosis of sickle cell disease
- 3. Steady state (no pain or baseline pain and ≥ 1 month from any hospital admission)
- 4. Receiving chronic transfusions (i.e regular transfusion every 4-8 weeks).

Exclusion Criteria

- 1. History of transfusion reactions not adequately managed by antihistamines
- 2. No available crossmatch compatible red cell units
- 3. Known G6PD deficiency
- 4. Hepato- or splenomegaly
- 5. Participation in another therapeutic trial
- 6. Pregnant or nursing
- 7. HIV positive

8. At investigator discretion for uncontrolled inter-current illness or social situation limiting compliance with study requirements.

9. Inability to speak and/or read English

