No alteration will be made to the labels on the RBC units. The expiration date, collection date, and any processing dates (e.g. irradiation dates) will not be obscured. Trained personnel at the adult Translational Research Unit will verify product and patient identity according to hospital-specific procedures. These personnel will be instructed to not divulge the patients' unit type. Other ancillary staff (other than those actually infusing RBCs), will be instructed not to seek to identify the G6PD status of the products transfused. The subjects themselves will not be informed of the identity of the labeled unit and will also be instructed not to seek to identify the G6PD status of the products they are receiving. However, as the key components of this study are objective, **inadvertent unblinding of the unit-status will not compromise the validity of the study data**.

Study Activities

24-72 hours prior to the 51Cr-labeled RBC infusion:

Draw 10mL of whole blood for type and screen

Day 1

- Physical exam by principal investigator or designee.
- Double-lumen Midline catheter placement by Interventional Radiology or VAT
- Provide daily diary
- Urine sample for urine pregnancy screen (females only)
- Vital signs will be checked for eligibility (subjects who are pregnant, have SBP >180 or <90mm Hg, DBP >100 or <50mm Hg, Heart rate <50 or >100, Temperature >100.4 F or feeling ill, will not continue study activities, and will be evaluated to be rescheduled).
- Informed consent for a blood transfusion, if not up to date
- Draw 10 mL of whole blood for CBCD, reticulocyte count, and hemoglobin electrophoresis.
- Draw 4 mL of whole blood for cell free hemoglobin.
- Draw 15 mL of whole blood for Hapto, Iron panel, BILI T/D, HSCRP, LDH, Ferritin, Iron Saturation, MPO, and NTBI.
- Clinic RN will transfuse the experimental RBC unit to the patient as the last unit of the red cell exchange or transfusion following hospital standard procedures
- Toward the end of the exchange/transfusion (about 30-45 minutes prior to completion), draw 30 mL from the unit into a syringe for chromium labeling. The syringe will be kept in a cooler once collected, and will be transported to Nuclear Medicine in the cooler for Chromium labeling once the transfusion is completed.
- Draw 6 mL of whole blood for in vivo chromium measurement (baseline- pre infusion).
- Infuse Chromium labeled blood into study subject.

Day 1 – post infusion

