5.2 Monitoring Subject Compliance

Pain and infection diary: The diary is adapted from previously published SCD studies.⁸⁷ Pain and infection symptoms will also be documented daily for 4 weeks along with the type, duration, and dose of antibiotics, if applicable. Daily, participants will rate pain on a numeric pain rating ordinal scale (0-10), indicate whether the pain was consistent with a "crisis," indicate whether they utilized a healthcare facility, and record the amount of opioids used. Infection symptoms will also be documented daily along with the type, duration, and dose of antibiotics, if applicable.

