Uncertainty about the optimal choice of methods and assumptions is best handled by relegating competing approaches to an important role in the domain of sensitivity analyses. The various sensitivity analyses will be used to evaluate the robustness/sensitivity of the study's main results to reasonable perturbations/modifications of the statistical methods and assumptions used. Results of the sensitivity analyses will be used to guide our level of trust in the main results.

[Reference: 2019 ICH E9-R1 addendum, "Estimands and Sensitivity Analysis in Clinical Trials". www.gmp-compliance.org/guidemgr/files/E9-R1_Step4_Guideline_2019_1203.pdf]

Exploratory analyses will be distinguished from confirmatory analyses. The purpose of exploratory analyses will be to generate new hypotheses or to refine hypotheses; p-values will not be used in exploratory analyses.

Statistical computations will be performed using software from Cytel (StatXact and LogXact), SAS Institute (SAS version 9.2), and Salford systems (CART).

Analysis Plan for Aim 1. The longitudinal analysis of the effects of treatment on 24-hour ⁵¹CR-labeled PTR of RBCs will rely on a generalized linear mixed-effects model which expresses mean response as a function of treatment regimen, treatment period, and occasion. The baseline PTR value will be treated as being one of the outcomes. The fitted model will be used to obtain parameter estimates that characterize the 24-hour trajectory of the mean response for each of the two regimens. Graphical figures will be used to display the resulting point- and interval-estimates.

Hypothesis testing. An F-test procedure will be used to test the null hypothesis "the treatment effect is exactly zero in the target population".

Missing data. For this main analysis, all enrollees with at least one post-exchange transfusion evaluation will be included. We anticipate that the main analyses will rely on an assumption that missing data values, if any, are attributable to ignorable causes (i.e., the mechanisms satisfy the "missing at random" (MAR) criteria.)

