Analysis Plan for Aim 2d. For each of the outcome variables [pain on an ordinal scale {0,1,2,..., 10}, occurrence of infection symptoms, and use of antibiotics (type, duration, dose)], a longitudinal analysis of the effects of treatment on mean response will rely on an analysis strategy similar to that described in Aim 1 for Estimation, handling Missing data, and Sensitivity analyses.

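### No diary entry is required before the study transfusion in either period, so Aim 2d has no period-specific starting value for pain or infection symptoms

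*Combined protocol and SAP*

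**What the plan says.** **Collection.** Section 9.1.1 makes a four-week daily diary the source of every Aim 2d outcome, and Section 5.2 agrees: "Pain and infection symptoms will also be documented daily for 4 weeks". Section 4.8 puts "Provide daily diary" in the Day 1 list. The only activity it gives for 24–72 hours before infusion is the type-and-screen draw. In the schedule table of the Schema, the diary row is blank in both pre-infusion columns and first marked at 1 hour. For period 2, Sections 3.1 and 4.8 repeat the same procedures after the washout and describe no diary run-in.

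**Analysis.** In Section 9.6, each Aim 2d outcome "will rely on an analysis strategy similar to that described in Aim 1" for estimation, missing data and sensitivity analyses. The Protocol Summary says of the crossover comparison: "The same approach will be used for Aims 2a – 2d". The Aim 1 model "expresses mean response as a function of treatment regimen, treatment period, and occasion", and Section 9.6 adds: "The baseline PTR value will be treated as being one of the outcomes". The pre-infusion baseline among the 15 occasions in Section 9.1.1 applies to blood samples.

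**Pain at entry.** Section 4.6 requires steady state, described as "no pain or baseline pain" plus a minimum interval since any hospital admission. This is an entry condition, not a recorded 0–10 score.

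**The concern.** The two periods begin well apart: 28 days of follow-up plus a washout of about 120 days gives roughly 148 days. Pain in sickle cell disease can differ between two such dates for reasons unrelated to the transfused unit. A value taken just before each study transfusion would show whether a participant began the two periods in a similar state, and would allow adjustment if not. The plan requires no such value.

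In a randomized crossover the loss is mostly one of precision. Here Section 9.3 assigns the sequence by unit availability, and the Study Design row of the Protocol Summary expects normal units to be likely first and deficient units likely second. Comparable starting states under the two regimens therefore cannot simply be assumed. Pain is also self-reported, so the reassurance in Section 4.8 that the key measures are objective does not extend to it. A starting value that is not collected cannot be recovered later.

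**Working it through.** **1. Is any diary entry scheduled before infusion?** The schedule has 11 visit columns.

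- Diary row: 8 marks (1, 24, 48 and 72 hours; weeks 1, 2, 3 and 4). None falls in the 24–72 hour pre-infusion, pre-transfusion or 5–30 minute columns.
- Adverse event row, as a check on table alignment: 9 marks, the same 8 plus pre-transfusion. The blank diary cell is therefore not a fault of text extraction.

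Required pre-infusion diary entries: 0 in period 1 and 0 in period 2.

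**2. Does anything else supply the value?** The Day 1 physical exam, the vital-sign and illness check, the pre-transfusion adverse event assessment and the steady-state criterion all bear on starting condition. None yields a 0–10 pain score or a diary infection item.

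**3. What can be estimated without it?** Take participant i's period 2 minus period 1 difference in mean pain. It contains (a) the shared period shift, (b) plus or minus the regimen effect, depending on sequence, and (c) that participant's own change in underlying pain.

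- With both sequences populated, comparing the differences between sequences cancels (a) and isolates (b). This is the work of the period term.
- Component (c) stays. It adds variance if unrelated to sequence, and bias if related to it.
- If nearly everyone follows one sequence, (a) and (b) are close to inseparable.

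**4. What would adjustment gain for pain?** The documents give no sample size, variance or correlation for Aim 2d, so r is an assumption. It is the correlation between the within-participant *difference* in baseline pain and the within-participant *difference* in 28-day mean pain. Stable patient level has already cancelled from both.

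- Inputs: n = 16 complete pairs. Differences analysed with a period effect leave 16 − 2 = 14 error degrees of freedom.
- Variance ratio for a known slope: 1 − r².
- Expected cost of estimating the slope (normally distributed covariate): 1 + 1/(14 − 2) = 1.083.
- SE ratio: √[(1 − r²) × 1.083].

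| Assumed r | 1 − r² | × 1.083 | SE ratio | SE reduction | Equivalent n (16 ÷ third column) |
|---|---|---|---|---|---|
| 0.3 | 0.91 | 0.986 | 0.993 | 0.7% | 16.2 |
| 0.5 | 0.75 | 0.8125 | 0.901 | 9.9% | 19.7 |
| 0.7 | 0.51 | 0.5525 | 0.743 | 25.7% | 29.0 |

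Break-even: (1 − r²)(13/12) = 1, so r² = 1/13 and r ≈ 0.28. Below this, adjustment raises the expected variance. At r = 0.3, the move from t(14) = 2.145 to t(13) = 2.160 uses up the gain: 0.993 × 2.160/2.145 ≈ 1.00, so the interval width is essentially unchanged.

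**The case against.** The best defence is that the plan does not break its own rules. Section 9.6 calls the Aim 2d strategy similar to that of Aim 1, not identical, and its baseline sentence names PTR only. Section 2.2 words Aims 2a and 2b as mean changes but Aim 2d as longitudinal scores. A reader might infer that the plan demands a baseline for Aim 2d and then fails to collect it. The text does not go that far, and a post-infusion-only analysis is compatible with it.

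A reader might also infer that the diary cannot hold a pre-transfusion entry. That is not established either. Section 4.8 lists handing out the diary ahead of the transfusion on Day 1, and most schedule marks coincide with diary review visits rather than first entries. An early entry is possible but not required, and a whole-day Day 1 entry would mix time before and after the transfusion.

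The tempting statistical reading is that drift passes straight into the regimen contrast, so that a bad period cannot be told from an effect of the unit. The period term answers this for shared drift when both sequences are populated. The Day 1 illness check, repeated in period 2, also screens out a grossly unwell start.

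Finally, Aim 2d is secondary, carries no power claim, and leaves Aim 1 unaffected. One to three days is a short baseline, and nothing in the documents shows that it would predict four weeks of infection symptoms or antibiotic use.

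These points limit the concern, but none supplies the missing starting value.

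**Conclusion.** The point holds in a limited form. No diary entry is required before the study transfusion in either period, so participant-specific differences in starting pain or infection symptoms between periods can be neither checked nor adjusted for. The regimen contrast remains estimable from post-infusion entries. The documents do not support calling Aim 2d unanalysable or its contrast necessarily biased.

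The precision at stake for pain is about 1%, 10% or 26% of the standard error at r = 0.3, 0.5 or 0.7. This assumes 16 complete pairs, both sequences populated, a normally distributed baseline difference and those values of r. Ignoring the cost of the slope would suggest 5%, 13% and 29% (√(1 − r²) = 0.954, 0.866, 0.714), which is too optimistic at this sample size. No precision gain is claimed for infection symptoms or antibiotic use.

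The firmer reason to act does not depend on r: with sequence set by unit availability, the investigators should be able to show whether the periods began alike. This is a cheap improvement to a secondary aim, and it can only be made before the data are collected.

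**What to change.** - In Section 4.8 and the schedule, hand out the diary at the 24–72 hour type-and-screen contact in both periods. That contact already exists, and the schedule already marks consent in the same column.
- Define that period's baseline as the entries completed before the study transfusion starts, and say how the Day 1 entry is split or timed.
- Report baseline pain and infection symptoms by regimen.
- In Section 9.6, name how the baseline enters the Aim 2d pain analysis: as a baseline occasion in the longitudinal model, or as the within-participant baseline difference. Fix the choice in advance.

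If the diary timing is left as it is, state in Section 9.6 that Aim 2d uses post-infusion occasions only.

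**Cost.** One to three extra diary entries per participant per period, a small change to the schedule, and one more parameter with 16 participants. If the baseline and outcome differences correlate below about 0.28, the adjustment slightly widens the pain interval. The comparability report keeps its value in that case.
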